### Limitations

National Medicaid data offer exceedingly large, reliable and widely used sources of information for comparative outcomes research. Although the data do not include some self-reported, recovery-oriented outcomes that might be available in prospective studies, outcomes available in our data such as avoidance of serious medical illnesses, premature death, and the need for psychiatric emergency services and hospitalization are valued by patients as important near-term outcomes that help make long-term recovery possible.

The analytic plans for Aims 1 and 2 involve only Medicaid financed patients, which is the dominant source of payment for individuals diagnosed with schizophrenia in the U.S. We will not be able to evaluate the comparative effectiveness of common pharmacological strategies in the relatively small patient population with private insurance. Similarly, we will not be able to study the comparative effectiveness of medication treatment strategies in uninsured patients. Yet the results of the proposed analysis will represent the experiences of most patients treated for schizophrenia in the United States including substantial representation of important groups, such as ethnic/racial minorities who are usually underrepresented in schizophrenia outcomes research, and patients with significant medical and mental health comorbidities who are often systematically excluded from such research.

Potential confounding is a concern in all observational comparative effectiveness research. We address potential confounding by treatment indication by restricting our analyses to second-line treatment strategies and comparable schizophrenia subgroups to create situations where the magnitude of potential confounding is expected to be limited due to a lack of strong evidence supporting one treatment option over others. The clinical diagnoses in claims data have the strong advantage of being the basis of real-world decision-making. In addition, propensity score methods will be used to minimize residual confounding from a large number of measured demographic and clinical patient characteristics.

## Appendices:

### Appendix 1: Exclusion Diagnoses

### Appendix 2: Variables included in propensity scores

## Appendix 1: Exclusion Diagnoses (Contraindications for clozapine, other antipsychotics, or life threatening)

Diagnosis	ICD-9-CM Codes*
Narrow angle glaucoma	365.02
Myocarditis	422.x, 391.2x, 398.0x
Neutrophil disorders	288.00-288.04, 288.09, 288.1x
Malignant neoplasms	140-205
Epilepsy, seizure disorders	345.xx
Alzheimer's and other cerebral degenerations	331.xx

\* x indicates inclusion of any 5th digit if available for a diagnosis code.

xx indicates inclusion of any 4th and 5th digits if available for a diagnosis code.

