### Data source and cohort identification

The data source will be national (45-state) Medicaid Analytic Extracts data (2001-2010). The cohort will consist of adults who are 18 to 64 years old and diagnosed with schizophrenia who initiate a new psychotropic medication after a period of stable antipsychotic treatment. Individuals who are 65 or older because will be excluded because they also have Medicare and receive pharmacy benefits through Medicare Part D.

Schizophrenia will be defined as  $\geq 2$  outpatient claims or  $\geq 1$  inpatient claim for schizophrenia [ICD-9-CM: 295] during 365 days of consecutive Medicaid enrollment immediately prior to the index date. Stable antipsychotic monotherapy will be defined by filled prescriptions for only one second-generation antipsychotic (excluding clozapine), and no other psychotropics, for  $\geq 90$  days immediately preceding the start of the index medication (t0). After the  $\geq 90$  days of stable treatment with a single second-generation antipsychotic, study patients will have had a change in therapy defined as (1) addition of a second antipsychotic or (2) addition of a different psychotropic drug class (antidepressant, mood stabilizer, or benzodiazepine). To ensure the patients are in active treatment there must be an active supply of antipsychotic medication on t0.

The eligibility criteria select a cohort of individuals that are likely to have schizophrenia, have received antipsychotic monotherapy prior to the index date, and are still experiencing problems for which a new psychotropic medication strategy was initiated. A 1-year period of eligibility prior to follow-up initiation ensures sufficient time to collect service use related covariates to characterize cohort members.

Patients with stable clozapine monotherapy will be excluded because clozapine is largely reserved for the most severely ill patients. Patients who implement more than one change in therapy at the index date (e.g., addition of a mood stabilizer and an antidepressant) will also be excluded.

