### Subgroups

From the base study population described above, 5 clinical subgroups will be defined based on the presence of psychiatric diagnoses during the 30 days prior to and inclusive of the treatment change under study (index date) and who have this same diagnostic code from more than one provider to increase the validity of the diagnostic groups. The subgroups will be defined by codes to capture 1) uncomplicated schizophrenia (with schizophrenia codes from at least 2 different providers and without any diagnoses that would qualify them for the other subgroups during the 365 days prior to the index date), 2) schizoaffective disorder (ICD-9: 295.7) as the most recent schizophrenia-spectrum diagnosis, 3) depressive (ICD-9: 293.83, 296.2, 296.3, 296.9, 298.0, 300.4, 311), 4) manic (296.0, 296.4-296.8), and 5) anxiety (293.84, 300.00-300.02, 300.09, 300.20-300.23, 300.29, 300.3, 300.7, 308.0-308.9, 309.21, 309.81, 312.39, 313.0, 313.21, 313.23). These subgroups are defined to reflect the reason for the change in treatment.

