### Comparators

Pharmacological treatment options for patients with schizophrenia who are nonresponsive to antipsychotic monotherapy will include (1) initiation of a second antipsychotic, (2) initiation of an antidepressant, (3) initiation of a mood stabilizer and (4) initiation of a benzodiazepine.

Within each clinical subgroup, treatment options may be refined by exclusions at the drug class or individual agent level. For example, antidepressants are generally not considered treatment alternatives in patients presenting with mania, but could reasonably be considered for patients in the remaining four schizophrenia subgroups: depression, anxiety, schizoaffective disorder, and uncomplicated schizophrenia. Unless it is not considered a reasonable treatment option for a specific subgroup, initiation of a new antipsychotic will serve as the reference category because it is a frequently recommended approach to improving treatment response and is a common treatment strategy across all of the clinical subgroups under study. A survey on the prescribing behaviors of clinicians who prescribe psychotropic medications for individuals with schizophrenia will inform these choices.

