#### AP treatment Initiation year

2002

2003

2004

2005

2006

2007

2008

2009

Diagnostic History, past year	ICD-9-CM Codes*
Depression	293.83, 296.2x, 296.3x, 296.9x, 298.0x, 300.4x, 311.xx
Anxiety	293.84, 300.0x, 300.2x, 300.3x, 308.3x, 309.21, 309.81, 313.0x, 313.2x, 313.89
Bipolar	296.xx (not 296.2x or 296.3x or 296.9x)
Substance use disorder	291.xx, 292.xx, 303.xx, 304.xx
Moderate/severe mental retardation	318.xx
HIV	042, 043, 044, 079.53, V08
Neoplasms	140.xx-239.xx (Exclude people with malignant neoplasms 140.xx-205.xx)
Diabetes	250.xx
Obesity	270.xx
Hyperlipidemia	272.0x-272.4x, 272.7x, 272.9x
White blood cell diseases	288.xx, 289.xx (exclude neutrophil d/o 288.00-288.04, 288.09, 288.1x)
Anemia	280.xx-285.xx
Drug-related dyskinesia	333.85
Hypertension	401.xx-405.xx
Ischemic heart disease	410.xx-414.xx
Pulmonary circulation diseases	415.xx-417.xx
Cardiac dysrhythmias	427.xx
Heart failure	428.xx
Cerebrovascular disease	430.xx-438.xx
Acute bronchitis and bronchiolitis	466.xx
Chronic bronchitis	491.xx
Pneumonia	480.xx-486.xx
Emphysema	492.xx
Asthma	493.xx
Appendicitis	540.xx-543.xx
Noninfectious enteritis and colitis	555.xx-558.xx
Diverticula of intestine	562.xx
Intestinal obstruction	560.xx
Chronic liver disease and cirrhosis	571.xx
Acute & chronic pancreatitis	577.0x, 577.1x
Cholelithiasis	574.xx
Acute kidney failure	584.xx
Chronic kidney failure	585.xx

Kidney infections	590.xx
Cellulitis and abscess	681.xx–682.xx
Osteoarthritis and allied disorders	715.xx
Intervertebral disc disorder	722.xx
Fractures, all sites	800.xx–829.xx
Fracture of neck of femur	820.xx
Poisoning by psychotropic medication	969.xx
Poisonings	960.xx–989.xx
Suicide and self-inflicted injury	E950-959
Intracranial injury	815.xx-854.xx
Severe cardiovascular diseases	401.0x-404.9x, 410.xx-416.xx, 425.xx-437.xx, 440.xx-447.xx
Schizophreniform	295.4x
Schizoaffective	295.7x

---

\* x indicates inclusion of any 5th digit if available for a diagnosis code.

xx indicates inclusion of any 4th and 5th digits if available for a diagnosis code.

Medication history, past year	Drug class
Psychotropic medication	
Antidepressants	SSRI/SNRI/mirtazapine, TCA and heterocyclic compounds, MAOI, trazodone-related antidepressants, bupropion
Mood Stabilizer	lithium, primary anticonvulsant, secondary anticonvulsant
ADHD medication	psychostimulants, alpha-agonists
Anxiolytic/hypnotics	benzodiazepines, GABA agonists, other newer or older anxiolytic/hypnotic

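### The seizure exclusion reaches only ICD-9-CM 345.xx, so a new anticonvulsant start after a seizure coded elsewhere can enter the mood-stabilizer arm with only partial adjustment

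*Combined protocol and SAP*

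**What the plan says.** Appendix 1 lists the exclusion diagnoses under the heading "Contraindications for clozapine, other antipsychotics, or life threatening". One row is "Epilepsy, seizure disorders", with the single code 345.xx. The footnote states that "xx indicates inclusion of any 4th and 5th digits if available for a diagnosis code", so the row covers everything under 345 and nothing outside it.

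The section on data source and cohort identification defines a qualifying change of therapy by drug class: a second antipsychotic, or "addition of a different psychotropic drug class (antidepressant, mood stabilizer, or benzodiazepine". It gives no rule on why the drug was prescribed. It describes the resulting cohort as patients who are "still experiencing problems for which a new psychotropic medication strategy was initiated". The Comparators section names "initiation of a mood stabilizer and (4) initiation of a benzodiazepine" among the four strategies and lists no agents.

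The one place that says what a mood stabilizer is comes in the medication-history table of Appendix 2: "lithium, primary anticonvulsant, secondary anticonvulsant".

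The Subgroups section infers the reason for the change from psychiatric codes: "These subgroups are defined to reflect the reason for the change in treatment". The uncomplicated subgroup needs schizophrenia codes from at least two providers and no diagnosis that qualifies for another subgroup.

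**The concern.** The row's label is wider than its code. In ICD-9-CM, the code set the plan uses, convulsions not specified as epilepsy fall under 780.3x. That code appears nowhere in the documents, and Appendix 2 has no seizure or convulsion covariate.

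Anticonvulsants serve two purposes. If the exposure uses the same class content as the covariate row, a patient with a recent seizure coded only 780.3x who starts one meets the mood-stabilizer definition, although the start answers a neurological event. The subgroup codes would not remove this patient, because a seizure code neither qualifies nor disqualifies anyone.

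A seizure gives a reason to start an anticonvulsant and no evident reason to add a second antipsychotic. Such patients would therefore tend to gather in one arm of a contrast whose other arm is the reference. If their risk differs, the contrast is confounded by something the claims record but the model omits. All-cause hospitalization and death, both secondary outcomes, are the most exposed.

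**Working it through.** The plan gives no figure on this point. The check therefore has two parts: the text, and a range under stated assumptions.

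**Which patients get through**

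1. A patient with any 345 code is excluded.
2. A patient already taking an anticonvulsant fails the rule of at least 90 days on one antipsychotic with no other psychotropic, provided anticonvulsants count as psychotropics there.
3. A patient coded only 780.3x who starts an anticonvulsant at t0 passes both rules. This is the remaining gap.
4. Appendix 2 contains correlates of seizure: substance use disorder, cerebrovascular disease, intracranial injury, poisonings, and past-year mood-stabilizer use. They adjust in part and do not replace the code itself.

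**How many episodes could be involved**

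Table 5 gives mood-stabilizer episodes of 9,954 (uncomplicated), 4,734 (schizoaffective), 1,296 (depression) and 2,107 (mania). The total is 18,091. The uncomplicated subgroup holds 9,954 / 18,091 = 55%. The affected share is not in the documents. At an assumed 1% to 10%:

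- all subgroups: 0.01 × 18,091 = 181 to 0.10 × 18,091 = 1,809 episodes
- uncomplicated: 0.01 × 9,954 = 100 to 0.10 × 9,954 = 995 episodes

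**Shift in one-year all-cause admission**

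Shift = (share in the mood-stabilizer arm − share in the reference arm) × risk difference between affected and other patients. Only the excess share counts. Both inputs are assumptions:

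- 1% × 10 points = 0.1 point
- 3% × 10 points = 0.3 point
- 5% × 20 points = 1.0 point
- 10% × 20 points = 2.0 points

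**Comparison with the precision of the contrast**

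Take the uncomplicated subgroup, mood stabilizer against second antipsychotic. Distinct patients are about 70% of episodes (Sample size section): 0.7 × 27,005 = 18,904 and 0.7 × 9,954 = 6,968. The plan states no event rate; I assume 30%.

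- All reference patients used: SE = √[0.21 × (1/18,904 + 1/6,968)] = 0.64 point. Detectable difference at 80% power, two-sided 0.05: (1.96 + 0.84) × 0.64 = 1.8 points.
- 1:1 matching, as in the Sample size section: SE = √[0.21 × 2/6,968] = 0.78 point. Detectable difference: 2.80 × 0.78 = 2.2 points.

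Both agree with the plan's statement that power in this subgroup is well above 80% for a 4% difference.

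A bias need not reach the detectable difference to mislead. With no true difference, the chance of a significant result is P(Z > 1.96 − shift/SE) + P(Z < −1.96 − shift/SE):

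| Shift (points) | All reference patients | 1:1 matched |
|---|---|---|
| 0.1 | 5.3% | 5.2% |
| 0.3 | 7.5% | 6.7% |
| 1.0 | 34% | 25% |
| 2.0 | 88% | 73% |

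At the low end the effect is negligible. It becomes serious only if both inputs are well above that end.

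**Primary outcome**

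Psychiatric hospitalization requires a first-listed mental disorder diagnosis, so an admission coded for a seizure would not count. Affected patients may still differ in psychiatric admission risk. The documents give no basis for a size or a sign.

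**The case against.** The strongest reply is that the list was not built to screen the reason for prescribing. Its heading speaks of contraindications and life-threatening illness, and leaving out a symptom code can be a deliberate choice for specificity. That stands. A reader might infer that the plan breaches its own exclusion rule, but the label may simply paraphrase category 345. The indication gap is a side effect of the list, and it remains on either reading.

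Second, the anticonvulsant content comes from a history covariate. The Comparators section allows exclusions at class or agent level, informed by a prescriber survey. This also stands, and it is why the point rests on an assumption. Agent-level exclusion would help only if it removed the agents that are also used for seizures.

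Third, safeguards exist. The 90-day rule, the exclusion of 345 codes, the need for psychiatric codes from more than one provider (within 30 days of the index date for most subgroups), the Appendix 2 correlates and the planned bias analysis all reduce the problem. It would be wrong to infer that the propensity score does nothing here. It adjusts partly. Bias analysis is meant for confounders that cannot be measured, whereas this one is available in the claims.

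Fourth, the range depends on assumptions and can overstate. A prior 780.3x claim does not make the seizure the reason for the drug, and some reference patients will also carry the code. A reader might take the 2.0-point upper end as bias in the primary result. The documents do not support that, since the figure concerns all-cause admission. Nor do they support the inference that the shift exceeds what the study can detect: under 1:1 matching the detectable difference of about 2.2 points is above the largest assumed shift. The documents also give no basis for asserting the same problem in the benzodiazepine arm; counts by arm would show it.

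**Conclusion.** The point holds as a minor gap in the code lists. The text is clear: 345.xx is the only seizure code, no convulsion code is excluded or adjusted for, and arms are set by drug class without a test of indication. A new anticonvulsant start in a patient coded only 780.3x can therefore sit in the mood-stabilizer arm for a non-psychiatric reason.

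The size is not known. Under an assumed excess share of 1% to 10% and a risk difference of 10 to 20 points, the all-cause admission contrast moves by 0.1 to 2.0 points before any partial adjustment through proxies. For the primary outcome neither size nor direction can be given.

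The conclusion rests on three assumptions: that 780.3x has its usual ICD-9-CM meaning, that the exposure uses the class content of the covariate row, and that affected patients are more common in the mood-stabilizer arm than in the reference arm. This is an improvement the sponsor could make at little cost. It is not a flaw that undermines the design.

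**What to change.** - Add 780.3x, recorded in the 365 days through t0, to the Appendix 2 propensity-score diagnoses for all arms. Include t0 itself, since the seizure and the drug start may share a date.
- Run one sensitivity analysis that also excludes these patients, reading the Appendix 1 row as 345.xx plus 780.3x, with the same look-back in every arm.
- Report the number of starts with a 780.3x code by arm and subgroup, so that the assumed share is replaced by a count.
- State whether the mood-stabilizer exposure uses the same agent list as the Appendix 2 covariate.

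The cost is one more covariate, one extra run, and, in the sensitivity analysis only, the loss of a small number of patients with an isolated convulsion code. Codes for other non-psychiatric uses of anticonvulsants are secondary; for migraine, treatment and prevention drugs are already a covariate in Appendix 2.

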## Appendix 2: Variables included in the Propensity Score

### Demographics

---

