### Secondary

We will also investigate time to index treatment discontinuation, time to introduction of another psychotropic medication, psychiatric emergency department visits, all-cause hospitalization, and death.

We will investigate adverse effects of medications including incidence of major cardiovascular events and diabetes mellitus.

Outcomes	
Death	Date of death will be defined by the Social Security Death Master File.
Psychiatric Hospitalization	Hospital claims will define inpatient admissions with a first listed mental disorder diagnosis (ICD-9:290-310). High levels of agreement between diagnoses in inpatient medical records and inpatient claims have been reported for several mental disorder groups, including schizophrenia (100.0%), major mood disorders (98.7%), alcohol dependence (97.8%), and drug dependence (96.4%). 
Psychiatric ED Visits	Emergency department claims are a reliable source of diagnostic information in relation to medical records and a valid source of illness severity information.  Emergency department visits in which the first listed diagnosis is a mental disorder (ICD-9-CM: 290-319) will be defined as emergency department mental health visits.
Self-Injurious Behavior	Deliberate self-harm will be defined by an E-code of E950-E958, excluding late effects of deliberate self-harm (E959), on any inpatient, emergency department, or outpatient claim. High positive predictive values have been reported. 
Diabetes Mellitus	One or more claims with a physician diagnosis of diabetes will define diabetes mellitus. Using self-reported diabetes status as the criterion standard, $\geq 1$ physician claim with any diagnosis of diabetes or a diabetes complication (ICD-9 codes: 295.00-2950.93, 357.2, 362.0-362.02, 366.41) has acceptable sensitivity (68.5%) and specificity (96.9%), and (kappa=0.76).  Sensitivity of 90% and specificity of 93% with self-reported diabetes. 
Cardiovascular Events:	Acute myocardial infarction (AMI) (ICD-9-CM: 410) or stroke (430-438, except 435) will be defined by diagnostic codes on inpatient claims of $\geq 3$ days in duration.  With this AMI definition 75% met criteria for definite or probable AMI on independent review of cardiac biomarkers, electrocardiograms, presenting symptoms, and medical history, and an additional 12% had a suspected AMI. 

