## Approach to confounding

Physicians make treatment choices in light of available clinical information and as a result there is a risk of confounding by clinical indication for the treatments under study. Our design minimizes confounding by indication by focusing on diagnostic subgroups. To further reduce confounding, we will control for a broad range of potentially relevant factors from claims histories. These factors will be identified in the 365-day period before drug initiation and used to calculate propensity scores. In addition we will conduct sensitivity analyses to estimate the extent of unmeasured confounding necessary to fully explain our observed findings and we will conduct instrumental variable analyses if a suitable instrument is identified.

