### *Propensity score estimation and application*

Propensity score methods involve two steps: estimation of the propensity scores and application of the propensity score. Estimation of the propensity scores involves decisions about which covariates to include in the prediction model of the propensity scores and what form the model should take. We will use expert opinion to select the variables to include in the propensity score. To estimate the propensity scores we will first use logistic regression including all baseline predictors occurring prior to treatment assignment. In addition, we will augment our analysis with another non-parametric method for building the propensity score model such as a generalized boosting algorithm implemented with regression trees. We will assess the sensitivity of our results to the choice of the propensity score model.

For the application of the propensity scores, we will use weighting by the odds to estimate the average treatment effect on the treated sample and weighting by the inverse probability of treatment weights to estimate the average treatment effect in the population.

We will examine the covariate balance using standardized differences in covariate means across the treatment groups after weighting, and address any significant imbalances.

**AIM 2 Heterogeneity of Treatment Effects:** Within the five subgroups, explore whether the comparative effectiveness and safety of alternative treatment strategies varies according to patient age and presence of a substance use disorder.

We will use similar Cox model techniques for the HTE analyses. First we will assess interaction of age and substance use variables with treatment. If such interactions are found, we will then perform analyses examining alternative treatment strategies stratified by age group or substance use.

The rationale for investigating patient age as a moderator of antipsychotic treatment effects follows from evidence that individuals early in the course of psychosis may respond differently to medications than people with more chronic illness. The rationale for investigating comorbid diagnosis of a substance use disorder as a moderator of treatment effects follows from evidence that people diagnosed with schizophrenia and comorbid substance use disorders respond more poorly to antipsychotic medications than those without comorbid substance use disorders.

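### The propensity-score list in Appendix 2 has no variable for the antipsychotic in use at t0 or for antipsychotic use earlier in the look-back year, although the claims data can supply both

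*Combined protocol and SAP*

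**What the plan says.** Under Approach to confounding, the plan says of its claims-based confounders: "These factors will be identified in the 365-day period before drug initiation and used to calculate propensity scores". Appendix 2, headed "Variables included in the Propensity Score", then lists demographics, Medicaid eligibility, diagnoses, medication history and service use.

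The past-year psychotropic rows cover antidepressants, mood stabilizers, ADHD drugs, anxiolytic/hypnotics and a short row of other psychiatric drugs. None covers antipsychotics. The only item labelled as antipsychotic is "AP treatment Initiation year", with categories 2002 to 2009. Phenothiazines appear only as antiemetics in the gastrointestinal row.

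The cohort section restricts antipsychotic use before t0. For at least 90 days a patient must have "filled prescriptions for only one second-generation antipsychotic (excluding clozapine), and no other psychotropics", and at the index date "there must be an active supply of antipsychotic medication on t0". It adds: "Patients with stable clozapine monotherapy will be excluded because clozapine is largely reserved for the most severely ill patients".

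Propensity score estimation and application leaves variable selection to expert opinion and says the logistic model will take in every baseline predictor that precedes treatment. It names no antipsychotic variable. It also says: "We will examine the covariate balance using standardized differences in covariate means across the treatment groups after weighting".

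**The concern.** Every patient enters on an antipsychotic, and the comparison is between things added to it. Which agent that is, and what was tried earlier in the year, may influence what the prescriber adds and may also predict outcome.

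The primary outcome is psychiatric hospitalization, and a history of several agents, clozapine or poor adherence plausibly marks a higher risk of it. The plan also says "We will investigate adverse effects of medications including incidence of major cardiovascular events and diabetes mellitus". The background antipsychotic is a medication that every patient is taking while those events are counted.

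If either factor differs between arms, weighting on the listed variables would balance it only so far as it correlates with them. A balance table limited to those variables would not show what was left. Unlike severity that claims cannot see, this can be adjusted for directly.

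**Working it through.** The plan states no figure on this point, so the check is mainly a reading of the list against the eligibility rules.

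**1. What eligibility fixes.** In the 90 or more days before t0 everyone takes exactly one second-generation antipsychotic, not clozapine, with supply on hand at t0. A yes/no variable for current antipsychotic use would therefore be constant and useless.

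**2. What eligibility leaves open.**
- The agent: any second-generation antipsychotic other than clozapine qualifies.
- Earlier use: the covariate window is 365 days and the stable period need only be 90, so up to 365 - 90 = 275 days (275/365 = 75%) are not covered by the single-agent rule. Switches, combinations, first-generation drugs or clozapine in that stretch are neither barred by the rule nor listed as covariates.

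**3. How the plan treats the other classes.** The same 90-day rule bars all other psychotropics, yet Appendix 2 still carries their past-year use. The plan thus does not regard 90 clean days as making earlier history irrelevant. The same reasoning applies to antipsychotics, the class common to every patient.

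**4. Whether the variables can be built.** The two have different sources. The agent at t0 follows from the fills that establish eligibility. The earlier pattern needs pharmacy claims from the rest of the year, which the drug eligibility rule need not use. Continuous enrolment is required over those 365 days, however, and Appendix 2 already takes its medication history from them.

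**5. What already adjusts in part.** Past-year psychiatric admissions, mental health emergency use, outpatient schizophrenia visits, other psychotropic use, and metabolic and cardiovascular diagnoses and drugs are all listed. They are proxies for severity and metabolic risk, not records of the agent or of treatment history.

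**6. Possible size, on assumed inputs only.** For one omitted binary factor with outcome relative risk RR and prevalence P1 and P0 in the two arms after weighting, the observed relative risk is multiplied by

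B = [P1(RR - 1) + 1] / [P0(RR - 1) + 1].

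None of these inputs is in the documents.
- RR 1.2, 25% vs 20%: 1.05/1.04 = 1.01
- RR 1.5, 30% vs 20%: 1.15/1.10 = 1.045
- RR 2.0, 40% vs 20%: 1.40/1.20 = 1.167

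The range runs from negligible to material, and nothing in the plan says where in it the truth lies, or which arm would be favoured. The formula is for risk ratios and only approximates the effect on a Cox hazard ratio.

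**The case against.** The strongest reply is that Appendix 2 need not be a closed list. The section on propensity score estimation refers to expert opinion and to all predictors before treatment, and Approach to confounding promises a broad range of factors. That stands to this extent: the plan permits these variables, and a reader who inferred that it contradicts itself or forbids them would go too far. But none of this text names them, and the appendix is titled as the variables included.

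Second, existing control is substantial: the single-agent restriction, the calendar year and the proxies above. This also stands. It reduces the problem without removing it.

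Third, the clozapine sentence might be read as showing that the plan treats antipsychotic choice in general as a marker of severity. It does not. It concerns clozapine only, which nobody can be taking as the stable agent at t0, and the Goal section calls clozapine rarely prescribed. It supports recording earlier clozapine use. The case for recording the agent at t0 rests instead on the safety outcomes and general plausibility.

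Fourth, a reader might infer that the balance check and the boosted propensity model are confined to the listed variables and so cannot help. The text does not say so; it names no other covariates for them either. The array analysis and the conditional instrumental-variable analysis are aimed at unmeasured confounders and do not replace adjustment for a measured one.

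Finally, a table row lost in conversion from PDF cannot be wholly excluded, though the medication block reads on without a visible gap or redaction.

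**Conclusion.** The point holds as an unexplained omission from the stated covariate list, cheap to repair. It should be addressed, but it does not undermine the design. Confidence is medium, because the variables are plausible confounders rather than demonstrated ones.

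Two stronger readings should be resisted. One is that the treatment comparisons are biased: the documents give no distribution of agent or antipsychotic history by arm, so size and direction are unknown, and the factors of 1.01 to 1.17 rest entirely on assumed inputs. The other is that the problem belongs mainly to the large uncomplicated-schizophrenia subgroup. A given imbalance produces the same bias factor whatever the sample size. Large groups only make a small shift more likely to reach significance, which says nothing about how much bias is present.

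**What to change.** Add to Appendix 2, to the logistic and boosted propensity models, and to the balance table:

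1. the second-generation antipsychotic in use at t0, identified from the eligibility fills, with rare agents grouped in the small subgroups;
2. antipsychotic history over the 365 days before t0, from the pharmacy claims that already supply the medication-history block: for example number of distinct agents, any earlier clozapine or long-acting injectable fill, and proportion of days covered. Count only fills before t0, so that a newly added second antipsychotic is not counted as history.

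If the experts choose to leave any of these out, one sentence of reasons in Appendix 2 is enough. The change deals with these measured variables only, not with unmeasured severity.

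The cost is a few covariates and possibly more variable weights in the smallest cells. The smallest in Table 5 is second antipsychotic in the anxiety subgroup: 611 episodes, or 0.70 × 611 = about 428 patients. At an assumed 40% risk in one arm, 428 per arm gives 80% power (two-sided .05) for a difference of about 9.5 points. If the variance rose by an assumed 5% to 20%, this would grow roughly with its square root, to between 9.75 and 10.4 points (for 20%: 9.51 × √1.20 = 10.4). The upper end slightly exceeds the 10.0 points quoted under Sample size for the smallest group, which is why rare agents should be grouped there.
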